SOC	System Organ Class
SOP	Standard Operating Procedure
UP	Unanticipated Problem
US	United States

STATEMENT OF COMPLIANCE

This clinical trial will be carried out in accordance with Good Clinical Practice (GCP) as required by the following:

- United States (US) Code of Federal Regulations (CFR) applicable to clinical studies (45 CFR Part 46, 21 CFR Part 50, 21 CFR Part 56, and 21 CFR Part 812)
- ICH E6

All key personnel (all individuals responsible for the design and conduct of this trial) have completed Human Subjects Protection Training.]

I agree to ensure that all staff members involved in the conduct of this study are informed about their obligations in meeting the above commitments.

Principal Investigator: **Print/Type Name**

Signed: Date: _____

PROTOCOL SUMMARY

Title: Rinovum Subsidiary 2, LLC. Disposable Stress Urinary Incontinence Device Efficacy and Safety Study

Précis: This study is an interventional, single arm, multi-center study. It will be conducted at sites in the northeastern United States. The protocol will be approved by Chesapeake IRB or applicable local IRBs. The sample size will consist of approximately 50 participants. Participants will undergo an initial control period in which preweighed pads will be worn for 7 consecutive days for 12 hours. This will be followed by device usage for 14 consecutive days where participants will wear both device and preweighed pads simultaneously. for 12 hours.

Objectives: The purpose of this study is to evaluate the efficacy and safety of an over-the-counter (OTC) disposable stress urinary incontinence (SUI) pessary device. Specifically, this study will evaluate the effectiveness of the pessary device by assessing reduction in urine leakage in approximately 50 women with Stress Urinary Incontinence (SUI). Efficacy will be assessed by mean pad weight gain per hour, reduction of stress urinary incontinence events per day, and a quality of life questionnaire. The safety of the OTC SUI pessary device will be evaluated by assessing all adverse events, including the results of urinalysis, vaginal swab, and vaginal examination.

Primary Objective: Demonstrate effectiveness of device usage

Important Secondary Objectives: Device reduces episodes of incontinence, improves quality of life, and is safe for over-the-counter (OTC) use.

Endpoints:

Primary Endpoint: Mean pad weight gain reduction per hour is >50% during the last 7 days of the treatment phase as compared to the baseline phase.

Important Secondary Endpoints:

- (1) Reduction in mean number of SUI episodes per day from the 7-day baseline period to the last 7 days of the 14-day device treatment period. Participants will record SUI episodes in the Study Diary during the baseline (7 days) and treatment (14 days) periods. Negative values are indicative of efficacious outcome.
- (2) Change in Quality of Life as Measured by the ICIQ-LUTSqol Quality of Life Questionnaire.

The Quality of Life Questionnaire to be performed at baseline, before, and after treatment phase of the study is based on 20 questions referring to areas which may have been influenced or changed by accidental urine loss and/or prolapse. These questions are assigned a value of, 1 = 'Not at all,' 2= 'Slightly,' 3 = 'Moderately,' or 4 'A lot.' Each area is then assessed on a scale of 1-10 to see how much it bothers them. The Questionnaire is scored by taking the average score of items and then multiplying that value by 25 to put scores on a scale from 0 to 100. A lower score is considered less impact to quality of life and a higher score reflects more impact to quality of life. In the same manner, a reduction in scores from baseline reflects improved quality of life. A reduction in

score of ≥ 3.7 is considered the Minimum Clinically Important Difference (MCID).

- (3) Evaluation of Adverse Event assessments to determine device is safe for use.

Important Exploratory Endpoints:

- (1) Participants can successfully use the device in accordance with the given Instructions for Use.
- (2) Participants will find the device comfortable enough to demonstrate compliance with the study procedures during the device treatment phase.

Population: Approximately 50 female participants over the age of 18 who have been physician diagnosed with Stress Urinary Incontinence; have a normal voiding history; are familiar with the use of tampons; and have had a Normal Pap Smear <36 months prior to study enrollment.

Phase: Efficacy and Safety

Number of Sites enrolling participants: 4

Description of Study Agent: A disposable stress urinary incontinence pessary device worn daily for 12 hours.

Endpoint Classification:	Efficacy and Safety Study
Interventional Model:	Single Group, Open Study
Masking:	Open Label
Primary Purpose:	Efficacy and Safety

Study Duration: 6-12 months

Participant Duration: 2 months

SCHEMATIC OF STUDY DESIGN

Prior to Enrollment (Screening)

Total N: Obtain informed consent. Screen potential participants by inclusion and exclusion criteria; obtain and document medical history. Confirm that participant symptoms indicate SUI diagnosis. Perform the urine pregnancy test (if applicable), urinalysis, vaginal examination and symptom evaluation to ensure participant has no active urinary or vaginal infection requiring treatment. A vaginal swab will be performed to establish baseline vaginal microflora. Perform usability and fit assessment test.

NOTE: Results of the SUI diagnosis assessment and fit assessment may deem participant ineligible for enrollment due to urge incontinence or mixed (stress and urge) incontinence diagnosis or poor /improper fit. To simulate OTC use, participants will be asked to perform self-selection and assess fit based on the product labeling prior to confirmation by the PI.

Enrollment/Visit 1 Time Point

Total N: Complete a questionnaire by the physician. Participant will also complete a baseline Quality of Life Questionnaire.

Participant will receive 14 preweighed pads to take home. Participant will perform control phase of study wearing pads for 12 hours/day for 7 consecutive days. Pads will be returned by participant for weighing and data collection.

NOTE: Results of the laboratory tests from the screening visit (pregnancy test, vaginal examination and urinalysis test) may deem a participant ineligible for enrollment due to positive pregnancy result, positive vaginal infection requiring treatment, or positive urinary infection requiring treatment, respectively.

Visit 2 Time Point

Total N: Urine pregnancy test, if applicable, to rule out pregnancy, vaginal examination, and symptom evaluation will be repeated to rule out any potential infection requiring treatment. Vaginal swab will also be repeated to evaluate changes in vaginal microflora. Quality of Life questionnaire will be repeated. Participants will be given 20 study devices and 28 preweighed pads to perform the treatment phase of the study. Participants will wear 14 devices and 14 pads simultaneously for 14 consecutive days. Pads will be returned by participant for weighing and data collection, and participants will record information regarding activity level and quality of life.

Visit 3 Time Point

Total N: Examination to determine final safety evaluation via investigator vaginal examination, vaginal swab, urinalysis, study questionnaire to collect final comments on device usage, and repeat Quality of Life questionnaire to evaluate changes in quality of life post treatment with device

Note (1): For pre-menopausal women, and women who have not undergone a hysterectomy, a Urine Pregnancy Test, usually to be done within 24 hours prior to study intervention is required. Results must be available prior to administration of study product, unless otherwise indicated by the physician.

2 INTRODUCTION: BACKGROUND INFORMATION AND SCIENTIFIC RATIONALE

2.1 BACKGROUND INFORMATION

Stress urinary incontinence (SUI) occurs predominantly among women. SUI is characterized by loss of urine resulting from increased abdominal pressures that occur when coughing, laughing, sneezing, running, lifting or walking. SUI causes quality of life degradation and contributes to women refraining from maintaining normal physical activities, and is also associated with low libido, vaginal dryness, dyspareunia.

Currently, there are several types of treatment options for SUI such as:

- Lifestyle/Behavioral changes including weight loss, pelvic floor strengthening exercises (Kegel), biofeedback, dietary changes and advisement to decrease fluid intake have been shown to have good results for motivated patients. However, it is difficult to compliance is relatively low.
- Non-surgical treatments, including Absorbent Pads; Pessary support devices (originally intended to support bladder prolapse) which elevate the vesico-urethral angle, devices that provide urethral occlusion, and weighted cones.
- Pharmacologic Therapy
- Surgical methods, including retropubic urethropexies, suburethral slings and periurethral injection of bovine collagen or carbon-coated beads.¹

Relevant clinical research demonstrates a need for nonsurgical options for treating SUI. Since the aging populations is growing, there are more instances of incontinence. Conservative treatment is fundamental as it is the only type of care many patients need or can undergo.²

¹Mark Deutchman, Meghan Wulster-Radcliffe. Stress Urinary Incontinence in Women: Diagnosis and Medical Management, 2005.

² Metcalf, et al. The Non-surgical Options for SUI – Is Any One Optimal?, 2016

Approximately 25% of premenopausal and 40% of postmenopausal women suffer from urinary incontinence, with the peak incidence beginning at around age 45-49. Of those dealing with urinary incontinence, 51% have stress urinary incontinence. Women that are Caucasian, have a BMI ≥ 30 kg/m², have been pregnant, and have had a vaginal delivery are at a higher risk of developing SUI. Intrinsic factors contributing to development of SUI include urethral musculature, blood flow and innervation. Extrinsic factors include degree of urethral support, patient weight, and degree of physical activity.

Multiple treatment methods have been studied, including surgery, pharmacological treatments, physical/behavioral therapy, and non-surgical options such as pessaries and intravaginal devices. While multiple treatment options exist, less than a third of women seek intervention in the first 12 months of experiencing SUI symptoms.

Surgical interventions have existed for over 100 years and are regarded as the most effective and durable treatment option for urinary incontinence; however, this surgery comes with physiological risks to the patient, high hospital costs, and productivity loss during recovery. While pharmacological options exist, they are not the standard of care in urinary incontinence treatment in the United States. While some topical pharmacologic are proven to resolve incontinence in some women, studies have shown both adrenergic drugs and oral hormonal treatments ineffective. One study revealed an 80% increase in incontinence in post-menopausal women. Not only have studies shown pharmacological treatments ineffective, they also carry side effects such as nausea, dry mouth, and fatigue. Having nonsurgical treatments are vital so that patients have reversible, safer, and less costly options to try before resorting to surgical and pharmacological treatments.

The primary nonsurgical and nonpharmacological options include behavioral and physical therapy, pessaries, and disposable, intravaginal devices, which are all relatively low risk and low cost. Pelvic floor muscle training combined with bladder training is effective; however, it is difficult for patients to comply with this treatment regimen and requires more extensive physician guidance. Understanding predictors of success will aid in patient counseling on treatment options. Menopausal status, education level, UI surgery status, and incontinence frequency were consistently identified as predictors of success across those that used behavioral therapy, pessaries, and a combination of both. Women that were post-menopausal, had higher education, no previous UI surgery, and had low incontinence frequency were found to have the most success when using nonsurgical treatments.

A study comparing cost utility of different treatment options revealed that incontinence pessaries were the most cost effective. Pessaries have been found to increase continence by 64-75%. While 50-75% of women decline pessaries when recommended, over three quarters of patients that use the pessary continue to use after one year. Studies have also revealed that women do not perceive any difference in the effectiveness of pessary treatment versus physical therapy treatment; however, pessary use is also associated with pain, irritation, UTIs and difficulty in physician fitting of the pessary.

A study performed to evaluate the efficacy and safety of a novel disposable intravaginal device for the treatment of SUI was performed at 2 sites in Israel. Sixty women were recruited and enrolled into the study and used the device for 28 – days after a 7-day control period. During the control period, preweighed pads were worn daily for 8 hours to determine a baseline for participants. This period was followed by a 28-day usage period. The last 14 days of the control period were used to allow for participants to find the right size device. The primary endpoint was

the percentage of women who achieved a $\geq 70\%$ reduction in pad weight gain (PWG) from the control period to the last 14 days of device usage. The results demonstrated that 85% of participants met the success criteria. The device was concluded to be easy to use, well-tolerated, and effective in reducing SUI³.

As is recommended in the Guidance for Industry and FDA Staff: Clinical Investigations of Devices Indicated for the Treatment of Urinary Incontinence, the Rinovum Subsidiary 2, LLC. SUI Device Pivotal Study will include the use of a voiding diary to document leakage occurrence daily. Also, as recommended in the guidance, the study will use pad-weighing to monitor efficacy of the device. The 24-hour test parameter will be used, but will be tailored to be in line with the amount of time the device will be used for treatment each day (12 hours). Participants will be provided with ziplock bags and mailers so that used pads can be collected daily and weighed by the site clinical team within 48 hours to determine the amount of pad weight gain (PWG). Note that more than 1 pad may be worn throughout each day depending on the amount of leakage protection required.

2.2 RATIONALE

This study is an interventional, open label, single-arm, clinical study in which participants will serve as their own controls. This study will enroll participants deemed eligible per the Inclusion/Exclusion Criteria. This study will evaluate the safety and effectiveness of the Rinovum Subsidiary 2 (RS-2) SUI pessary device by assessing reduction in urine leakage in approximately 50 women with SUI. Efficacy will be assessed by reduction in pad weight gain, frequency of stress urinary incontinence events, and a quality of life questionnaire. The study design consists of a control/no treatment period for each subject and a device treatment period for each subject.

The participants in this study will use the pre-weighed pads daily for 12 hours per day to obtain baseline control urine leakage data. This baseline will be for 7 consecutive days. The pads may be changed as necessary during this time. The same participants will use the device, and the same pre-weighed pad method for 14 consecutive days during the treatment period. Participants will be asked to schedule the treatment phase during a time when they will not have an interruption in the treatment phase such as menstrual cycle or travel. Patients will be asked to perform the treatment period within 21 days. In both the non-treatment and treatment phase of the study, the preweighed pads will be collected and weighed for use in calculating pad weight gain (PWG).

Safety analysis will include results of urinalysis, vaginal swab, vaginal examination, and evaluation of adverse events.

Usability of the device will be assessed by the PI at Enrollment where the participant will insert the device while following the Instructions for Use. The PI will examine the device inside the vagina to ensure successful placement and fit.

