7.3 STUDY SCHEDULE

Prior to enrollment, screening questions, a medical file review, a physical examination, pregnancy test (if applicable), urinalysis, and a human factors and a fit assessment will be used to determine/assess whether a participant meets the eligibility criteria. A vaginal swab shall be performed to establish baseline vaginal microflora. These activities must be performed within 1 week of enrollment. Informed consent will be obtained prior to any screening procedures. The human factors and fit assessment will include the following:

- Participant will perform self-insertion and removal in accordance with the IFU under supervision of physician
- Participant will provide feedback regarding the fit of the device based on the IFU description of proper fit without input of the physician
- Physician will verify device is a proper fit for participant after participant performs self-insertion (if physician determines the device is not a good fit for the participant, the participant may be terminated from the study)

Enrollment/Visit #1 schedule shall consist of the following:

- Provide participants with a description of what to expect with the study
- Participant will complete a Quality of Life Survey
- Provide the patient with a Baseline Study Diary for them to keep track of their leaking patterns for the first phase of the study
- Physician will administer 14 preweighed pads for the patient to wear for 7 consecutive days.
- Record any adverse events

NOTE: all worn pads will be placed in preweighed, double sealed, ziplock bags and returned to the clinical site via mail within 48 hours of use by the participant for weighing throughout the entirety of the study

NOTE: to minimize time between pad wearing and pad weighing, participants will be mailing back all worn pads immediately upon completion of the 7-day wear to the site. The site will record the pad weights in the Pad Weight Log form.

Visit #2 schedule shall consist of the following:

- Update Medical History, if applicable
- Perform a urine pregnancy test, if applicable
- Perform a vaginal swab for vaginal microflora assessment
- Assess for any symptoms of active vaginal infections requiring treatment (if a patient is symptomatic of a vaginal infection, they may be treated and enrolled at a later date once vaginal infection has resolved).
- Collect Baseline Study Diary from participant
- Go over a series of questions with participants
- Repeat the Quality of Life questionnaire

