10.4 Statistical Hypotheses and Data Description

1. Type 1 Error and Multiplicity Concerns:

The inferential tests for the one primary and two secondary endpoints were initially conceived to be one-sided using alpha=0.05. Since the sponsor wishes to use the success of all three for labeling and marketing purposes, a Bonferroni adjustment for multiple comparisons will be employed. Thus, statistical significance will be indicated for each endpoint if the p-value is less than 0.0167.

2. Primary Endpoint:

There is one primary endpoint, for efficacy. The objective is to show that reduction in the mean pad weight gain per hour is >50% in the treatment period. Thus, the null hypothesis is that the mean weight gain reduction per hour is <=50%, and the alternative is that it is >50%, from the control period (no device) to the treatment period (women wearing the device). The data values will be computed for each woman as:

[(total weight of all pads worn during the treatment period/hrs. pads are worn during treatment)

minus

(total weight of all pads worn during the control period/ hrs. pads are worn during control)]

The above quantity divided by
(total weight of all pads worn during the control period/ hrs. pads are worn during control)

This resulting quantity is then multiplied by 100.

Ex. Subject's total pad weight for control period is 140 grams. Pads were worn for a total of 100 hours. Weight/hr. is $140/100 = 1.4$ g/hr. Subject's total pad weight for treatment period is 60 grams. Subject wore pads for 100 hours. Pad weight per hour is $60/100 = 0.6$ g/hr. Difference, treatment – control is $0.6 - 1.4 = -0.8$ g/hr. For the percent change, $100 * (-0.8/1.4) = -57.143\%$. Therefore the reduction in pad weight gain is 57.143%.

The null hypothesis will be that the mean reduction in pad weight gain per hour is less than or equal to 50%, with the alternative that it is greater than 50%. If the raw percentage change data appear to be normally distributed, a paired t-test will be used to test the hypothesis. If not, see section 10.6 (2).

The precision method will be utilized to determine success. The precision approach creates a lower bound for a confidence interval that is higher than the reference, in this case 50%. This 50% standard was chosen based on the FDA guidance document.

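### Women are asked to keep menses and travel out of the device phase but not the control week, so menstrual fluid on control pads can count as baseline leakage

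*Combined protocol and SAP*

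**What the plan says.** Each woman is her own control: a pads-only week comes first, then 14 days of pads plus device.

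- **Device phase.** Section 2.2 asks women to choose a time "when they will not have an interruption in the treatment phase such as menstrual cycle or travel". It adds: "Patients will be asked to perform the treatment period within 21 days".
- **Control week.** The same section says only "This baseline will be for 7 consecutive days". The Visit 1 list in Section 7.3 says "Physician will administer 14 preweighed pads for the patient to wear for 7 consecutive days". Neither of these, nor the design schematic, nor Section 4.1, sets a condition on menses or travel.
- **Who can enrol.** Section 5.1 admits women over 18 with no upper age limit. Note (1) to the schematic foresees menstruating participants: "For pre-menopausal women, and women who have not undergone a hysterectomy, a Urine Pregnancy Test" is required.
- **Primary endpoint.** Section 10.4(2) takes the treatment-minus-control difference in pad weight per hour and divides it by "total weight of all pads worn during the control period/ hrs. pads are worn during control". No days are removed for bleeding, and Section 10.6 plans no covariates.
- **Tampons.** Section 7.5 rules out a tampon together with the device. It says nothing about the control week.

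**The concern.** A scale cannot tell menstrual fluid from urine. Fluid on control pads enlarges the denominator. If the device phase is placed to avoid bleeding, the later absence of that fluid is read as a device effect. The comparison is before against after, always in the same order and against a fixed 50% bar, so no concurrent group would show the same drop and reveal the artefact. The request may also add to the problem, because a woman who needs 14 bleed-free device days may well begin just after a period, which puts the period in the week before. At stake is the error rate of a test whose result the sponsor intends to use for labeling and marketing (Section 10.4(1)).

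**Working it through.** **The plan's own example.** Section 10.4(2) has 140 g over 100 h in control (1.4 g/h) and 60 g over 100 h in treatment (0.6 g/h). The reduction is 1 − 0.6/1.4 = 57.143%, as stated. Suppose menstrual fluid adds a fraction f to control weight and nothing else changes:

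- f = 10%: 1 − 0.6/1.54 = 61.0%
- f = 25%: 1 − 0.6/1.75 = 65.7%
- f = 50%: 1 − 0.6/2.10 = 71.4%

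**General form.** Measured reduction = 1 − (1 − R)/(1 + f), where R is the true reduction. At R = 50%, an affected woman shows 54.5%, 60.0% or 66.7% for f = 10%, 25% or 50%.

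**Calendar check.** Assumed, not from the documents: a 28-day cycle, bleeding on days 1 to 5, and the device phase directly after the control week.

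- A bleed-free 14-day device phase can start on cycle days 6 to 15, which gives 10 possible starts.
- Bleeding days in the preceding control week, in order of start day, are 5, 5, 5, 4, 3, 2, 1, 0, 0, 0. So 7 of 10 schedules (70%) have bleeding in the control week, with a mean of 25/10 = 2.5 days.
- Without the request, a randomly placed control week overlaps bleeding with probability (7 + 5 − 1)/28 = 39%, with a mean of 7 × 5/28 = 1.25 days.
- Over cycles of 26 to 30 days and 4 to 6 bleeding days, the share is 54% to 100% with the request and 33% to 46% without it.

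**Effect on the test.** From Sections 10.3 and 10.4: n = 50, null value 50%, one-sided 0.0167, and SD 18 from within the planned 15 to 20. Assumed: a true mean of exactly 50%, a share p of all women affected, and f as above. The mean shifts by p × (50 − 50/(1 + f)) points, with standard error 18/√50 = 2.55.

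| p | f | Mean shift (points) | False success, noncentral t | False success, simulation |
|---|---|---|---|---|
| 0 | 0 | 0 | 1.7% | 1.7% |
| 8% | 10% | 0.36 | 2.3% | 2.3% |
| 12% | 10% | 0.55 | 2.8% | 2.7% |
| 20% | 25% | 2.0 | 8.7% | about 9% |
| 35% | 25% | 3.5 | 21.7% | about 23% |

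The simulation runs slightly higher because dividing by 1 + f also narrows the spread among affected women.

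**Second set of inputs, in grams.** Take 1.4 g/h × 84 h = 117.6 g of urine in the control week, 25% of women affected, and 10, 20 or 40 g of fluid on their pads. Affected women show 53.9%, 57.3% or 62.7%, and the mean shifts by 1.0, 1.8 or 3.2 points. False success is 4.4%, 9.0% or 22.4% at SD 16, and 3.7%, 6.7% or 15.1% at SD 20.

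**What the shares imply.** Dividing p by the overlap rates of 70% and 39%, 8% affected needs about 11% to 20% of the cohort to be cycling and bleeding onto pads. The 20% case needs about 29% to 51%, and the 35% case about 50% to 89%.

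**The case against.** - **Direction.** Participants must have tampon experience (Section 5.1), and women who had difficulty with tampons are excluded (Section 5.2). Fluid absorbed by a tampon does not reach the pad, so the bias shrinks. If a tampon also reduced leakage, which the documents do not address, control weight would be too low and the bias would reverse. Pads are also worn only 12 hours a day. A reader might infer that the gap necessarily inflates false success, but the documents do not support that. What stands is that fluid reaching control pads acts in the device's favour.
- **Size.** The documents give no share of cycling women, no fluid weight and no cycle timing, and the 140 g is an illustration. The error rates apply only at a true mean of exactly 50%, whereas the plan expects 60%. This all stands. At a true 60%, f = 25% would still show 1 − 0.40/1.25 = 68% in an affected woman.
- **A request, not a bar.** Menses are discouraged in the device phase, not excluded, and the stated aim is to avoid interrupting it. Bleeding there would count against the device. This tempers the point, but the control week still has no matching request.
- **Travel.** It too is restricted in one phase only, but nothing in the documents shows which way that would move leakage.
- **Infection at Visit 2.** A reader might infer that a woman symptomatic at Visit 2 keeps a baseline worn with discharge. Section 7.3 says "they may be treated and enrolled at a later date once vaginal infection has resolved". Enrollment is Visit 1, so this can equally mean a fresh Visit 1 and a new control week. The wording is unclear, but a contaminated baseline is not established.
- **Cost of dropping days.** Under Sections 4.2 and 10.1, a woman with 6 of the last 7 days leaves the Per Protocol population, and Sections 5.4 and 10.6 keep recruiting until 50 such women complete. Leaving out flagged days without adjusting that rule would be expensive. This stands and shapes the fix.
- **Diary content.** The diary forms are not in the documents, so a bleeding item may already exist. The analysis plan uses none.

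**Conclusion.** The asymmetry is real and no other section cures it. Followed as written, the plan can put non-urine fluid in the denominator of a single-arm test against 50%, and under the calendar assumptions its one-sided request makes bleeding in the control week more likely (70% against 39%). The bias probably favours the device, but its size is unknown. False success runs from about 2.3%, barely above the nominal 1.7%, to about 23%, depending on the assumed share of women affected and weight added. Control-week tampon use could remove or reverse it. This supports a cheap improvement that should be made before enrolment. It does not support a conclusion that the primary result would be invalid.

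**What to change.** 1. **Sections 2.2 and 7.3.** Make the same scheduling request, for menses and travel, for the control week. Travel is included only to keep the two phases comparable.
2. **Both diaries.** Record menstrual bleeding and tampon use daily (yes/no). Keep menses distinct from other bleeding, because Section 2.3 lists vaginal bleeding or spotting as a device risk.
3. **Section 10.4(2).** Prespecify an analysis that leaves out the pad weight and hours of flagged days in both phases. State its role (primary or sensitivity) and the minimum number of days that must remain.
4. **Sections 4.2 and 10.1.** State that a day left out for this reason does not by itself remove a woman from the Per Protocol population.
5. **Section 7.3, Visit 2.** Reconcile the infection wording with enrollment at Visit 1, so that it is clear which control week serves as baseline.

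The cost is protocol and diary wording, a few extra pads, and a delay of up to about two to three weeks for some pre-menopausal women. No procedure is added. The record has to be in place before enrolment, because bleeding days that were not recorded cannot be reliably recovered afterwards.
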